18.2 Analysis Policies

A statistical analysis plan will be completed before the data are analyzed in an unblinded fashion. Due to clinical interest in departures from both sides of the null hypothesis, all test statistics will be twosided. The trial results will be reported according to guidelines specified in the CONSORT statement^{121,122}. A flow diagram describing screening, recruitment, randomization, dropout, and vital status will be included in the primary manuscript. Adverse events and efficacy data will be presented by the two treatment groups. Adherence, dropout, and lost-to-follow-up will be carefully examined across the two treatment groups. Analyses of safety will be based on data from all randomized patients who received at least 1 dose of study drug. All primary analyses will be based on intent-to-treat (ITT) principles using all randomized participants.

18.2.1 Controlling Type-I Error

The primary endpoint of change in peak VO2 from baseline to 24 weeks will be evaluated at the twosided 0.05 level. A conservative approach will be taken with the multiple analyses on key clinical subgroups. For subgroup analyses, a significance level of 0.001 will be required for statistical significance. Thus, subgroup analyses will be considered exploratory unless the p-value from an interaction test is smaller than 0.001.

18.2.2 Interim Analyses for Efficacy

There will be no interim analysis for efficacy due to the short duration and small size of the trial.

18.3 Randomization

A permuted block randomization scheme will be created with varying block sizes stratified by the presence or absence of atrial fibrillation. Enrollment of patients with atrial fibrillation is planned to be limited to 58 patients (30% of study population). Once 58 patients with chronic atrial fibrillation have been enrolled, the DCC and DSMB will review the characteristics (atrial fibrillation versus sinus rhythm) of all patients enrolled and will increase this limit if needed to insure adequate enrollment to address the primary endpoint. Once a patient has completed the screening and baseline period and evaluation for inclusion/exclusion criteria, the randomization process will begin. Patients will be randomized to receive one of the 2 treatment regimes with equal probability (1:1), via a Web based system (WebEZ). On the day of randomization, after the patient has successfully met all inclusion and exclusion criteria, the investigator or designee will log into the on-line WebEZ randomization system to obtain the assigned kit randomization numbers for the patient. The WebEZ system will also be used for re-supply of the site.

18.4 Statistical Comparisons of Baseline Factors

For continuous variables, baseline factors will be compared across groups using mean (standard deviation) and median (25th and 75th percentiles) summary measures. For categorical variables, baseline factors will be summarized using counts and percentages with statistical comparisons based on the Pearson's chi-square statistic. Given the size of this proof of concept trial, the potential for inequitable distributions of baseline characteristics between the treatment groups exists. We have pre-specified subgroup analysis for those variables most likely to impact response to PDE-5 inhibition. Randomization will be stratified by site and by rhythm (presence of atrial fibrillation), primarily to insure that there are equal numbers of sildenafil and placebo treated patients in the group without atrial fibrillation who will undergo MRI. If significant differences in baseline characteristics exist, an analysis adjusted for these characteristics will be performed.

18.5 Specification of the Primary Analyses

A general linear model with the change in peak VO2 measured at 24 weeks compared to the baseline peak VO_2 as the response variable and predictor variables including a treatment indicator and the baseline measure of peak VO2 will be used in the primary analysis. The treatment effect will be determined by the point estimate and 95% confidence interval for the treatment indicator.

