9.3 Concomitant Therapies

Current guidelines for management of DHF stress control of hypertension, rate control for patients with atrial fibrillation, avoidance of tachycardia in patients in normal sinus rhythm, maintenance of sinus rhythm, use of diuretics and revascularization if diastolic dysfunction is thought related to ischemia⁴⁴. These recommendations are based on consensus opinion as there have been few clinical trials in DHF and no therapy has been proven to improve clinical outcomes (see section 4.3). Thus, treatment with agents to control blood pressure and maintain volume status is expected but no specific concomitant therapies are specified.

Study exclusion criteria outline drugs which can not be used due to concern over drug interaction (see exclusion criteria, section 8.3). These include nitrate preparations as well as alpha antagonists or cytochrome P450 3A4 inhibitors or serum protease inhibitors for HIV. If the patient develops clear indication for nitrates (angina which can not be managed with alternative antianginals), the patient will need to be withdrawn from the study. If the need for nitrates is emergent or urgent, the treatment assignment in the patient should be obtained emergently from the DCC so that patients treated with placebo could start treatment with nitrates immediately. If the patient was on active therapy, the exact time after the last dose of sildenafil when nitrates can be safely administered is not well defined. Although plasma levels of sildenafil at 24 hours post dose are much lower than at peak concentration, it is unknown whether nitrates can be safely co-administered at this time point. Thus, it is recommended that nitrates should not be administered to any patient previously on active study drug prior to 5 days after the last dose of sildenafil. Should there be an urgent need for nitrate administration, they should be administered in a monitored inpatient setting.

In patients with a history of volume retention or hypertension, standard therapy will specify a low sodium diet but no specific instructions regarding diet will be provided as part of the study. Daily aerobic exercise is recommended for patients with HF as tolerated but no specific recommendations for activity will be provided as part of this study.

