12.3 Blinding of Study Personnel

All enrolled patients will be assigned a study number and study drug (placebo or sildenafil) will have an identical appearance and will be allocated according to a predetermined randomization scheme. The DCC will allocate study drug and the study staff will not have access to information regarding whether the patient is on active or placebo therapy. As sildenafil may commonly have characteristic benign (enhanced erectile function) or rarely adverse (priapism) side effects in male patients, study subjects will be encouraged at consent and enrollment not to discuss any non-adverse changes in sexual function with the study staff. However, all patients will be assessed for adverse events at the serial study visits as outlined above. If a patient has experienced an adverse effect likely or potentially attributable to the study drug, the decision to discontinue the drug will be made without unblinding the patient or the study staff unless deemed urgent to care of the patient. In this case, the DCC will supply the information and the patient will be removed from the study.

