18. STATISTICAL CONSIDERATIONS

18.1 Sample Size and Power Considerations

18.1.1 Primary endpoint: Change in peak VO₂ (\triangle VO₂)

No previous study has characterized the standard deviation of the ΔVO_2 in a study population similar to that planned here where DHF patients are studied and strict entry criteria and a screening cardiopulmonary exercise test (CPXT) are used to minimize enrollment of patients with non-cardiac dyspnea and select for patients who can perform near maximal exercise (RER≥1.0). Patients who are unwilling or unable to perform at this level of exercise will not be eligible for enrollment. This requirement will reduce variability in both the primary endpoint (Δ peak VO₂) and the secondary endpoint measuring submaximal exercise (\alpha 6MW). Recognizing the lack of data relevant to the planned study population, we have based power calculations on the SD for the ΔVO_2 observed in randomized clinical trials (RCT) in SHF where ΔVO₂ was a primary (SD=2.7 ml/kg/min)¹¹¹ or secondary (SD≈2.7 ml/kg/min) ^{112,113} endpoint and on limited RCT data in DHF⁵⁰ (SD=1.3 ml/kg/min; [name], personal communication). A range of withdrawal due to death at 6 months was also estimated based on a large RCT in DHF (<2%)⁴⁷ and community based observational studies in DHF (13-16%)^{7,11}.

Power	85% Power			90% Power			analysis indicates that a sar	
	TE = 1.0 ml/kg/min	nin ml/kg/min	ml/kg/min ml/	TE = 1.0 ml/kg/min 172	TE = 1.2 ml/kg/min 120	TE =1.5 ml/kg/min	1.2 ml/kg/min in ΔVO_2 with	
SD=2.0	146					78		
SD=2.5	228	158	102	266	186	120	SD of ΔVO_2 =2.5 ml/kg/min. account for up to 25% mis	
SD=3.0	326	228 146	382	266	172	data, the projected sample s		
							is approximately 215 patients In patients with SHF, a si dose of sildenafil resulted in	

The relationship between power, effect size (mean difference in ΔVO_2) and SD of the ΔVO_2 using a two sample t-test and a two-sided alpha of 0.05 is shown in the table assuming 85% and 90% power. This

dose of sildenafil resulted in statistically significant increases in

TE=treatment effect (difference in Δ in peak VO2); SD = standard deviation of Δ in peak VO2

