18.6 Specification of the Secondary Analyses

A Wilcoxon test will be used to calculate the P(X<Y) and the p-value for the clinical composite score endpoint. Multivariate rank-ordered data will be analyzed according to the worst-rank approach of Lachin¹²³. A mixed model repeated measures (MMRM) analysis will be used to compare differences in the slope of peak VO2 and 6MW distance across the two treatment groups¹²⁴. Contrast estimates of differences in slopes of treatment by time (along with confidence intervals) will be used to estimate the treatment effect. The validity of this model in terms of meeting modeling assumptions will be assessed via standard modeling diagnostics and goodness-of-fit measures. Based on the MMRM framework, missing peak VO2 and 6MW distance data will not be imputed. Sensitivity analyses will be conducted using an inverse probability weighted method to account for missing data¹²⁵.

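### The primary model in 18.5 is in effect an observed-case analysis of patients with a week-24 exercise test, which does not match the promise in 18.2 to use all randomized participants

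*Protocol*

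**What the plan says.** - **Primary model (18.5).** The response is one number per patient: "A general linear model with the change in peak VO2 measured at 24 weeks compared to the baseline". The predictors are treatment and baseline peak VO2. The section has no rule for a patient without a week-24 value.
- **Population (18.2).** "All primary analyses will be based on intent-to-treat (ITT) principles using all randomized participants".
- **Sample size (18.1.1).** The calculation uses a "two sample t-test and a two-sided alpha of 0.05". The total is raised to "account for up to 25% mis" (the wording is split around a table; missing data are meant) and "is approximately 215 patients". The same section cites six-month death rates of under 2% in a large randomized trial and 13-16% in community cohorts.
- **Secondary analyses (18.6).** An MMRM compares slopes of peak VO2 and 6-minute walk distance. Within that framework "missing peak VO2 and 6MW distance data will not be imputed". An inverse-probability-weighted sensitivity analysis follows. A worst-rank method is cited for rank-ordered data.
- **Data collection (13.1).** Peak VO2 is measured at week 12 as well as week 24.
- **Leaving the study.** Under 9.3, if nitrates become clearly indicated, "the patient will need to be withdrawn from the study". Under 12.3, after urgent unblinding, "the DCC will supply the information and the patient will be removed from the study". Under 13.3, subjects who drop out for any reason are encouraged to complete as many study procedures as they will agree to.

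**The concern.** Two stated rules do not fit together. Section 18.2 names all randomized participants as the primary population, and 18.5 names a model that only patients with a week-24 test can enter. The sample-size section takes the second view: it computes an evaluable number and inflates it, so patients with missing data are counted as lost to the primary analysis.

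What is at stake is the estimate from the trial's only primary test. Patients who die, worsen or stop the drug are unlikely to be a random subset. If the reasons for missing week 24 differ between sildenafil and placebo and relate to early response, the observed-case difference is biased. Some of these patients will have a week-12 test, which the primary model cannot use. If the conflict is left open, the choice between observed-case and likelihood-based estimates could be made after the data are seen.

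**Working it through.** **1. Reproduce the plan's sample size.** Inputs from 18.1.1: effect 1.2 ml/kg/min, SD 2.5, 85% power, two-sided alpha 0.05. Allocation is 1:1 (section 6).

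- Normal approximation per arm: 2 x (1.960 + 1.036)^2 x 2.5^2 / 1.2^2 = 77.9, so 78 per arm and 156 in total.
- The exact noncentral-t calculation gives 79 per arm, 158 in total. This is the protocol's table entry.
- Inflation for 25% missing: 158 / 0.75 = 211, consistent with approximately 215.
- The 90% power entry, 186, would need 186 / 0.75 = 248. The 85% entry is the one that fits.

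The arithmetic is sound, and it treats patients without week-24 data as not analysed.

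**2. Count who is left out of 215 and check power** (t-test, effect 1.2, SD 2.5).

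| Missing at week 24 | Left out | Analysed | Power |
|---|---|---|---|
| 25% (ceiling, 18.1.1) | 0.25 x 215 = 53.75, about 54 | about 161 | 85.8% |
| 10% (18.1.2, 18.1.3, tertiary endpoints) | 0.10 x 215 = 21.5, about 22 | about 193 | 91.3% |
| None | 0 | 215 | 93.9% |

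Deaths alone, on the rates cited in 18.1.1, would account for 0.02 x 215 = about 4 patients up to 0.16 x 215 = about 34. Power stays at or above the planned 85% throughout.

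**3. Bias by hand, under assumptions that the protocol does not give.** Suppose patients without a test did worse than those tested by a shift s, the same in both arms, and the missing fractions are m(active) and m(placebo). Then

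all-randomized difference = observed difference - s x [m(active) - m(placebo)].

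With an observed difference of 1.2 and s = 1 to 3 ml/kg/min:

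- 30% missing on active, 20% on placebo: 1.2 - 0.1s = 1.1 to 0.9. The observed-case estimate is 0.1 to 0.3 too high.
- 20% and 30%: 1.2 + 0.1s = 1.3 to 1.5. It is 0.1 to 0.3 too low.
- 25% in both: no bias.

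**4. Illustrative simulation.** Assumptions: 215 patients, SD 2.5, true effect 1.2, about 25% missing, correlation of the week-12 and week-24 changes 0.5-0.65, every dropout has a week-12 test.

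| Dropout mechanism | Observed-case estimate | Likelihood analysis with week 12 |
|---|---|---|
| Placebo dropout follows poor week-12 result, sildenafil random | 0.68 to 1.05 | 1.18 to 1.21 |
| Reversed between arms | 1.47 to 1.55 | 1.20 to 1.21 |
| Same mechanism in both arms | 1.20 | not needed to remove bias |
| Random | no bias | no bias; SE about 3-5% smaller |

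The likelihood analysis recovers 1.2 partly by construction, since dropout depends only on a value that it sees. The low estimates need strong dependence. A separate calculation (logistic dropout, 25% missing, no baseline adjustment) shows that about 0.71 (correlation 0.65) or 0.83 (correlation 0.5) requires dropout odds roughly 5.5 to 6 times higher per SD of worse week-12 change, in one arm only. An estimate of 0.96 (correlation 0.65) requires about 1.9 times.

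**The case against.** The best reply is that 18.5 never says completers or observed cases. A linear model for the 24-week change can be fitted to imputed data, the no-imputation sentence in 18.6 is tied to the MMRM, and missing-data detail is commonly left to the analysis plan that 18.2 announces. Baseline-adjusted analysis at one time point is also a standard primary method, valid if missingness depends only on arm and baseline. This stands in part: a later plan could supply a rule, and the model is respectable. It does not remove the conflict, because the protocol itself fixes the model, the population and a sample size that counts missing patients as lost.

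Several stronger readings are tempting but unsupported:

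- **A quarter of patients will be lost.** 25% is an upper limit. Other endpoints assume 10%, the trial-based death rate in 18.1.1 is under 2%, and section 15 notes that event rates in trials are generally lower.
- **The estimate will be 20-40% too small.** That follows only from strong one-arm dependence, which nothing in the protocol supports. The direction can also reverse.
- **Week-12 data are discarded.** They are a secondary endpoint and enter the MMRM in 18.6.
- **No missing-data sensitivity analysis covers the primary endpoint.** The weighting sentence sits under the secondary heading but is not expressly limited to secondary endpoints, and its cited method concerns pretest-posttest studies.
- **9.3 and 12.3 contradict 13.3.** They can be read together, since 13.3 covers dropout for any reason. The wording is unclear rather than contradictory, and the protocol gives no basis for a count.
- **An MMRM would deliver all randomized patients.** It would not: anyone with no post-baseline test still drops out, and deaths have no week-24 value.

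**Conclusion.** The point holds as a mismatch between the primary model and the stated primary population, of moderate severity and not a must-fix. Between about 22 (10% missing) and 54 (25% missing) of 215 randomized patients would be outside the primary analysis on the protocol's own allowances. There is no loss of planned power.

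Whether bias follows, how large it is and which way it runs cannot be determined from the documents. The range of about 0.7 to 1.55 around 1.2 rests on assumed correlations and on dropout that depends on week-12 response differently by arm. With the same mechanism in both arms there is essentially none. The case for change is that a week-24 contrast using week-12 data needs a weaker missing-data assumption than the observed-case model, at little cost.

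**What to change.** 1. **18.5:** make the primary estimate the week-24 treatment contrast from an MMRM on the week-12 and week-24 changes, with visit as a category, baseline peak VO2 as covariate and unstructured covariance. The MMRM in 18.6 compares slopes and does not give this contrast, so it cannot simply be promoted.
2. **18.6:** state that the inverse-probability-weighted sensitivity analysis applies to the primary endpoint, and add a worst-rank sensitivity analysis for deaths before week 24.
3. **18.2:** say how patients with no post-baseline test are handled. The minimum alternative is to keep the linear model and call the primary set observed cases, which is transparent but leaves any bias in place.
4. **9.3, 12.3 and 13.3:** reconcile the wording on withdrawal or removal from the study with continued study assessments. No clinical rule needs to change.

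The cost is wording only. No new data or patients are needed, and the weighting and worst-rank methods are already cited. The downside is that the MMRM assumes missing at random, and it projects patients who stop before or at the week-12 dose step from those who continued. The sensitivity analyses should probe this. The choice should be fixed before unblinding.

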12.2 Randomization Procedures

After the patient has been consented and has completed the screening studies, patients meeting meeting the entry criteria based on the screening studies will undergo baseline studies and then be randomized. Randomization will be performed via a web based system (WebEZ) Randomization will be stratified by site and by the presence or absence of atrial fibrillation.

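### The primary model in section 18.5 names none of the randomization strata, section 18.3 disagrees with 12.2 and 18.4 on whether site is one, and the extra adjusted analysis in 18.4 picks covariates by baseline significance

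*Protocol*

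**What the plan says.** **Primary model (18.5).** The response is change in peak VO2 from baseline to 24 weeks, and "predictor variables including a treatment indicator and the baseline measure of peak VO2 will be used in the primary analysis". The treatment effect is read from the point estimate and 95% confidence interval of the treatment term.

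**Strata.** Section 12.2: "Randomization will be stratified by site and by the presence or absence of atrial fibrillation". Section 18.4 says the same, and gives as the main reason that the arms should be equal in size among patients without atrial fibrillation, who undergo MRI. Section 18.3, which specifies the allocation scheme, mentions rhythm but not site: "A permuted block randomization scheme will be created with varying block sizes stratified by the presence or absence of atrial fibrillation".

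**Further adjustment (18.4).** "If significant differences in baseline characteristics exist, an analysis adjusted for these characteristics will be performed". For categorical factors there are "statistical comparisons based on the Pearson's chi-square statistic"; for continuous factors only summary measures are listed. No significance level and no list of candidate covariates is given.

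**The concern.** Stratified permuted blocks force the arms to be nearly balanced on the strata. If a stratum predicts the outcome, that balance removes part of the chance variation in the treatment difference. A model without the stratum still counts its contribution as residual noise, so it reports a standard error larger than the true one. The interval is then too wide and power is lost for no return.

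Two related matters sit alongside this. The strata cannot be carried into the model until the protocol says what they are, and three sections do not give one answer. And choosing covariates because they differ significantly between randomized arms selects on chance imbalance, when what makes a covariate useful is its relation to the outcome.

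**Working it through.** **1. The plan's own sample size.** Section 18.1.1 uses a "two sample t-test and a two-sided alpha of 0.05 is shown in the table assuming 85% and 90% power". For a difference of 1.2 ml/kg/min and SD 2.5 at 85% power:

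- Normal approximation: n per arm = 2 × (1.960 + 1.036)² × 2.5² / 1.2² = 77.9, so 78 per arm, 156 in all.
- t-test: 79 per arm, 158 in all, as printed. All 16 readable cells of the table reproduce with the t-test.
- Allowing for 25% missing: 158 / 0.75 = 211, close to the stated 215. Conversely 215 × 0.75 = 161 evaluable, with about 86% power.

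The sample size is sound and does not depend on this point.

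**2. Reported against true standard error.** Let R² be the share of outcome variance explained by the strata, with n patients split 1:1 and near-perfect balance within strata:

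- model without strata reports SE ≈ 2σ/√n
- true SE ≈ 2σ√(1 − R²)/√n

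With σ = 2.5 and n = 160, the reported SE is 5/12.65 = 0.395. The true SE is 0.395 at R² = 0, 0.395 × √0.9 = 0.375 at 10%, and 0.395 × √0.8 = 0.354 at 20%. The actual two-sided type I error is the chance that |Z| exceeds 1.96/√(1 − R²): 5.0%, 3.9% and 2.8%.

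**3. Simulation.** Balance is imperfect in small site-by-rhythm cells, so this was checked with 3,000 simulated trials per setting, using blocks of 2 or 4 within site by rhythm. Assumed, not in the protocol:

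- 9 sites
- 27% atrial fibrillation (the cap of 58 over 215)
- 160 evaluable patients
- SD 2.5, taken as the SD left after baseline adjustment
- R² split equally between rhythm and site

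| R² of strata | Type I error, no strata | Type I error, rhythm + site | Power at 1.2, no strata | Power at 1.2, rhythm + site |
|---|---|---|---|---|
| 0% | 4.7% | 4.6% | 85.0% | 84.7% |
| 10% | 4.2% | 5.1% | 85.4% | 87.6% |
| 20% | 3.1% | 4.8% | 88.1% | 92.1% |

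At R² = 20% under the null, the model without strata reports a mean SE of 0.395 against an empirical SE of 0.351, a ratio of 1.125. At R² = 0 the two agree (0.394 and 0.394). The gain in power from adding the strata is −0.3, 2.2 and 4.0 points. Simulation error is about 0.4 points on type I error, √(0.05 × 0.95/3000), and 0.65 points on power, √(0.85 × 0.15/3000).

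**4. The strata side by side.** Sections 12.2 and 18.4 give site and atrial fibrillation; 18.3 gives atrial fibrillation. Section 18.3 does not say that rhythm is the only stratum, but it is the section that defines the scheme, and as written it describes a different list.

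**5. The significance trigger.** With k independent baseline tests at an assumed level of 0.05, the chance of at least one significant result under proper randomization is 1 − 0.95^k: 23% for k = 5, 40% for k = 10 and 64% for k = 20. The protocol gives neither k nor the level.

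**The case against.** The strongest reply is that the model is left open. The predictors are introduced by the word *including*, section 18.2 promises a statistical analysis plan before unblinded analysis, and the handling of site is commonly settled there. That is fair as far as it goes, and a plan not shown may already add the strata. It does not alter the fact that the section specifying the primary analysis names two predictors and neither stratum, and no analysis plan can make 12.2, 18.3 and 18.4 agree.

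The second reply is that the harm is conditional and small. This stands. Nothing in the protocol shows that rhythm or site predicts change in peak VO2 once baseline is in the model, and 18.4 justifies the rhythm stratum mainly by MRI numbers, not prognosis. If the strata explain nothing, nothing is lost.

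Three stronger readings are tempting, and the document supports none of them:

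- A reader might infer that the primary result is biased or its type I error inflated. Neither follows: the estimate is unbiased and the error runs in the conservative direction.
- A reader might infer that 18.4 lets baseline tests choose the primary model's covariates. It provides for a further analysis; baseline peak VO2 is in the primary model unconditionally, and 18.2.1 fixes the primary test at two-sided 0.05.
- A reader might measure the problem by shrinking the SD in a power formula by √(1 − R²). That shows what any useful covariate would gain; the flaw here is the gap between reported and true standard error, which step 2 of the working isolates.

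**Conclusion.** The point holds as a modest, nearly free improvement. The stated primary model does not reflect the stratified allocation, and to the extent that the strata are prognostic its interval is too wide: by about 12% at the top of the range tried, and not at all at the bottom. These sizes rest on the assumed number of sites, share of atrial fibrillation and R²; only the direction of the error is independent of them.

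The disagreement over site is a plain inconsistency that must be settled, since it decides what belongs in the model. The trigger in 18.4 is a poorly fixed rule for a supportive analysis: its covariates would depend on chance, and without a level, a list or a test for continuous factors it cannot be applied reproducibly. Its consequence is an extra estimate of uncertain meaning, not a changed primary one.

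**What to change.** - **12.2, 18.3, 18.4:** state the same strata in all three, matching what the web randomization system is programmed to use.
- **18.5:** add atrial fibrillation as a fixed term. If site is a stratum, add it too, either as a random effect or as a fixed effect with small sites pooled by a rule set before unblinding.
- **18.4:** drop the significance trigger. Replace it with one supportive model whose covariates are listed in advance because they are expected to predict change in peak VO2, and describe baseline balance without tests.

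The cost is wording and a few degrees of freedom. With nine sites as fixed effects, that is one for rhythm and eight for site, out of 160 − 3 = 157 left after intercept, treatment and baseline. In the simulation with non-prognostic strata this cost 0.3 points of power, within simulation error. The sample size stays at about 215.
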